## List of Abbreviations

ADE	=	Adverse Device Effect
AE	=	Adverse Event
CA	=	Competent Authority
CIP	=	Clinical Investigation Plan
CTU	=	Clinical Trial Unit
EC	=	Ethics Committee
eCRF	=	electronic Case Report Form
GCP	=	Good Clinical Practice
GDPR	=	General Data Protection Regulation
HIRUZ	=	Health, Innovation and Research Institute UZ Ghent
ICF	=	Informed Consent Form
IEC	=	Independent Ethics Committee
ISO	=	International Organization for Standardization
LSLV	=	Last subject, last visit
PI	=	Principal Investigator
SADE	=	Serious Adverse Device Effect
SAE	=	Serious Adverse Event
SOP	=	Standard Operating Procedure
USADE	=	Unanticipated Serious Adverse Device Effect
PSS	=	Perceived Stress Scale
VAS	=	Visual Analog Scale
VR	=	Virtual Reality

## Synopsis of the clinical investigation

TITLE	The effects of relaxation using Virtual Reality, by forensic psychiatric patients. A randomized crossover clinical trial
ACRONYM	VRelax study
SPONSOR	UGent-UZGent
COORDINATING INVESTIGATOR	[name]. [name]
NAME OF DEVICE	
 
- PICO VR bril, de software is VRelax
 
- Embrace plus
 

MANUFACTURER	
 
- PICOXR.com
 
- Vrelax.com
 
- Empatica.com
 

STUDY DESIGN	Cross-over randomized controlled trial
CENTER(S) / COUNTRY(IES)	UZGent en PC Sint-Jan Baptist, in Zelzate, Belgium
OBJECTIVES	
Primary Objective  To determine whether VR relaxation has a significant effect on a person's stress level. This will be assessed, among other measures, through a change in the VAS relaxation score, where an average improvement of 0.5 out of 10 is considered clinically relevant. With this study, we aim to gain insight into the effects of VR relaxation on both subjective and objective stress, heart rate, and other physiological parameters.
 
Secondary Objectives  We will also examine changes in the VAS score for happiness, where an average improvement of 0.5 out of 10 is considered clinically relevant. We aim to assess whether VR relaxation has a greater relaxing effect compared to standard relaxation. Additionally, we want to gain insight into the feasibility of implementation and evaluate the user-friendliness of the application. Furthermore, we intend to identify the most suitable types of VR environments for relaxation and investigate whether the effect may be greater in patients with intellectual disabilities or other psychiatric disorders.

ENDPOINTS	
Primary Endpoint A change in the VAS score for relaxation, where an average improvement of 0.5 out of 10 is considered clinically relevant.
 
Secondary Endpoints A change in the VAS score for happiness, where an average improvement of 0.5 out of 10 is considered clinically relevant.

STUDY DURATION	3 years
NUMBER OF PATIENTS	54
INCLUSION CRITERIA	Be admitted for at least 4 months as a forensic psychiatric patient within medium or high security, at Sint-Jan Baptist in Zelzate.
EXCLUSION CRITERIA	Acute psychosis, acute mania, epilepsy, pacemaker, balance disorders, individuals in the acute withdrawal phase of substance or alcohol abuse, severe cardiac abnormalities, serious eye disorders, pregnancy.
PROCEDURES	Relaxation therapy with or without VR, heart rate measurements using the Embrace Plus device, and questionnaires.
COMPARATIVE DEVICE	none

### 3. Title of the Clinical Investigation

**The effects of relaxation using Virtual Reality in forensic psychiatric patients. A randomized crossover clinical trial.**

**Acronym:** VRrelax study

---

### 4. Single Identification Number of the Clinical Investigation

**Eudamed number:** ONZ-2023-0315

---

**5.2 Device Name and Manufacturer**

- Pico VR headset – [Picoxr.com](http://Picoxr.com)
- VRelax software – [Vrelax.com](http://Vrelax.com)
- Embrace Plus – [Empatica, Empatica.com](http://Empatica.com)

---

**5.5 Financing of the Clinical Investigation**

This study is funded by PC Sint-Jan Baptist and partially supported by a research grant from the Brothers of Charity.

---

**6. Introduction****6.1 Background Information**

Stress is a well-established factor in the onset and persistence of burnout, anxiety, mood, and psychotic disorders. Sleep disorders further predispose individuals to, and exacerbate, these psychiatric symptoms. Individuals with mental health problems tend to have higher (social) stress reactivity and impaired stress recovery, which is compounded by sleep disturbances and sleep deprivation.

Relaxation can reduce stress, thereby potentially improving mental health symptoms. Moreover, stress-reducing interventions may enhance quality of life, social functioning, and occupational performance. While current stress-reducing interventions appear effective, they often require mental effort—such as focus and concentration—which may be compromised in patients.

To bridge this gap, a new e-Health application called **VRelax** has been developed. VRelax is a virtual reality self-management tool designed to reduce stress. It requires significantly less effort than traditional relaxation exercises due to its immersive qualities and has an immediate effect on perceived stress and emotional mental states.

Following a comprehensive literature review on the potential applications of Virtual Reality (VR) in forensic psychiatric populations—published in November 2021 in the *Tijdschrift voor Psychiatrie*—this study will be the first to assess the effects of VR-based relaxation in such a setting. The study aims to determine whether VR relaxation provides added value for both patients and staff, and how best to implement this technology within the hospital's operations.

Given that VR environments can simulate highly realistic situations that forensic psychiatric patients would otherwise be unable to experience due to their restricted freedoms, VR offers a powerful tool that addresses the limitations of confinement. The highly immersive nature of the application also benefits patients who are unable to engage in traditional relaxation exercises due to limited imagination or empathy skills.

This study will investigate the short- and medium-term effects of VRelax on both acute and chronic stress and compare these effects to a standard relaxation exercise of the participant's choice (Treatment As Usual, TAU). The study is based on previous work by Veling et al. (2021), in which the same VRelax application was tested in an outpatient setting.

---

## 6.2 Rationale of the Clinical Investigation

There is a clear need for stress-reducing interventions in forensic psychiatry. The ability of VR environments to create highly realistic scenarios—unavailable to patients due to their limited freedom—makes VR an especially valuable tool in this context. Moreover, the immersive experience supports patients who are otherwise unable to perform standard relaxation techniques due to cognitive or emotional limitations.

This study will be the first to test VRelax in a residential forensic psychiatric setting. During the COVID-19 pandemic, several small-scale studies were conducted using VRelax to reduce stress among healthcare workers in general hospitals (Nijland et al., 2021).

## Hypothesis of the Clinical Investigation

1. VRelax will reduce acute stress: the PRE-VAS score will be higher than the POST-VAS score.
2. VR relaxation will have a greater relaxing effect than standard relaxation: VAS scores and biomarkers will reflect a stronger relaxation effect.
3. VRelax will also reduce chronic stress through a cumulative effect, meaning the post-intervention PSS score will be lower than the pre-intervention PSS score.
4. There will be a difference in the acute effect over time; in other words, as the number of sessions increases, habituation or boredom may occur for both standard and VR relaxation. This will be measured by a decreasing difference between pre- and post-VAS scores per individual over time.

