## **7. Objective of the Clinical Investigation**

### **7.1 Primary Objectives**

The main objective is to examine the relaxing effect of VRelax. We aim to measure the magnitude and duration of the effect and assess the difference compared to standard relaxation exercises. What is the immediate effect, and what is the long-term impact? Is there any habituation? Which physiological parameters are most influenced?

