## **13. Methodology**

### **13.1 Study-Specific Procedures**

The study consists of two blocks of 10 sessions: one block with VR and one without. Each participant thus serves as their own control.

The control sessions take place in the VR room, seated, with a total duration of 30 minutes (including 20 minutes of relaxation of their choice, e.g., reading, listening to music, watching a short film, body scan, etc.). The selected relaxation method is recorded for each session.

The VR sessions also take place in the VR room, seated, with a duration of 30 minutes (including 20 minutes of VRRelax with one or more 360° videos of the participant's choice). Guided meditation sessions are excluded, as they require the eyes to be closed. The selected videos are recorded per session.

Before and after each session, stress is assessed using VAS scores for stress/tension and happiness. At the beginning and end of each 10-session block, general stress levels are measured using the Perceived Stress Scale (PSS). After the final session of each block, a structured qualitative interview is conducted regarding the user experience. All groups receive the same pre- and post-intervention assessments.

During each relaxation session, physiological parameters are also measured using the Embrace Plus device ([www.Empatica.com](http://www.Empatica.com)), including heart rate, heart rate variability (HRV), respiratory rate, skin conductance, and skin temperature.

---

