**1 - (VAS score before / VAS score after)**

Descriptive statistics (mean, standard deviation, minimum, and maximum) will be computed for demographic, clinical, and outcome variables.

VAS scores for relaxation and happiness, as well as physiological parameters (heart rate, HRV, skin conductance, respiration), will be compared using **paired t-tests** between pre- and post-session time points.

Perceived Stress Scale (PSS) scores will also be compared between pre- and post-therapy blocks (each block consisting of 10 sessions) using a paired t-test.

To estimate the difference in effect between the VR treatment and standard relaxation, a **mixed model multilevel regression analysis** will be used. The model will include:

- Time (before vs after)
- Treatment (VR vs standard)
- Group (1 vs 2)
- Interaction term: Time × Treatment  
(with random intercept for “participant”)

The **interaction between time and treatment** is the primary parameter of interest.

Finally, **carry-over effects** will be examined by comparing VAS scores and physiological parameters between session 1, session 5, and session 10 using paired t-tests (S1 vs S5 and S5 vs S10).

---

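### Hypothesis 4 measures habituation only by a shrinking pre-post VAS difference, which a cumulative benefit can also cause, and the plan does not say how the two will be told apart

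*Combined protocol and SAP*

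**What the plan says.** **Hypotheses.** Hypothesis 4 expects that "as the number of sessions increases, habituation or boredom may occur for both standard and VR relaxation", and gives one measure for it: "This will be measured by a decreasing difference between pre- and post-VAS scores per individual over time". It offers no other reading of a falling difference. Hypothesis 3, in the same list, states: "VRelax will also reduce chronic stress through a cumulative effect, meaning the post-intervention PSS score will be lower than the pre-intervention PSS score". It is stated for VRelax only, whereas hypothesis 4 covers both conditions.

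**Objectives.** Section 7.1 asks, under the primary objectives, "Is there any habituation"? Section 7.2 says the trial should inform whether VR is implemented and whether the expense is justified.

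**Data.** Section 13.1: "Before and after each session, stress is assessed using VAS scores for stress/tension and happiness". The PSS is taken at the start and end of each 10-session block, and a structured user-experience interview follows each block.

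**Analysis.** Section 16.2 has a mixed model with time (before or after a session), treatment, group and time by treatment. It has no term for session number. The only comparison across sessions is under carry-over: "comparing VAS scores and physiological parameters between session 1, session 5, and session 10 using paired t-tests", for S1 vs S5 and S5 vs S10. It does not say whether pre-session, post-session or change scores are compared, and it does not mention hypothesis 4.

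**The concern.** The scale is read here as tension, because hypothesis 1 expects that "the PRE-VAS score will be higher than the POST-VAS score". A patient who arrives less tense has less room to improve within a session. If the cumulative benefit of hypothesis 3 reaches the pre-session score, the within-session difference can fall for a reason opposite to boredom, and the stated measure would record both cases in the same way.

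What is at stake is the answer to a question posed under the primary objectives, and its use in the implementation decision of section 7.2. Because hypothesis 3 is stated only for VRelax, a misreading would tend to count against VR more than against standard relaxation.

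**Working it through.** The plan gives no figure for habituation, so there is none to reproduce. The check has four steps.

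**1. When does the difference shrink without habituation?** Let the session effect be the same at every session: post = a + b × pre. Then pre − post = (1 − b) × pre − a. If mean pre-session VAS falls by F points over the block, the difference shrinks by (1 − b) × F. A proportional effect is the case a = 0. A parallel fall is b = 1, and the shrinkage is then zero.

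**2. How often would that be flagged?** Inputs from the documents: 54 patients and 30% dropout (section 16.1), so 54 × 0.7 = 37.8, or 38 completers; SD 0.74 for VRelax (section 16.1). Assumptions: F = 1 point, half of it by session 5; 0.74 is the SD of a change score, independent across sessions; change scores are what the S1 vs S5 and S5 vs S10 tests compare; two-sided 5% per test. The standard error of each comparison is 0.74 × √2 / √38 = 0.170. The last column is the simulated chance that at least one test is significant in the shrinking direction; repeat runs differ by about one percentage point.

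| Slope b | Shrinkage by S10 | Shrinkage per test ÷ 0.170 | Falsely flagged |
|---|---|---|---|
| 1.0 (parallel) | 0 | 0 | about 5% |
| 0.8 | 0.2 | 0.1 / 0.170 = 0.59 | about 17% |
| 0.6 | 0.4 | 0.2 / 0.170 = 1.18 | about 40% |
| 0.4 | 0.6 | 0.3 / 0.170 = 1.76 | about 71% |

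**3. Can the stated measure separate the explanations?** A second illustration used assumed values: mean pre-session tension 5, between-person SD 1.5, error SD 0.8, 38 completers, difference compared at S1 and S10.

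| Scenario | Pre-session mean, S1 to S10 | Difference, S1 to S10 | Flagged |
|---|---|---|---|
| True habituation: effect 40% weaker, arrival level unchanged | 5.0 to 5.0 | 2.0 to 1.2 | about 84% |
| No habituation: constant 40% reduction, 2-point fall in arrival level | 5.0 to 3.0 | 2.0 to 1.2 | 87% |
| The same, 1-point fall | 5.0 to 4.0 | 2.0 to 1.6 | 34% |
| The same, 0.5-point fall | 5.0 to 4.5 | 2.0 to 1.8 | 12% |
| No habituation: parallel fall of 0.5 to 2 points, scale stops at 0 | 5.0 to 4.5–3.0 | 1.98 to 1.95–1.73 | 3% to 16% |

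The first two rows give the same difference. The pre-session mean tells them apart, and it is collected.

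**4. Does adjusting for pre-session VAS solve it?** Only in part. With ten sessions, b = 0.6, a 1-point fall and no habituation, the trend in the raw difference was called habituation in 86% of simulated trials, and the trend in post-session VAS adjusted for pre-session VAS in 3%. But error in the pre-session reading weakens its coefficient. If r is its within-person reliability, the adjusted trend is biased by about b × (1 − r) × F in the improving direction. With b = 0.8, F = 1 and error SD equal to the within-person SD (0.8 each), r = 0.64 / (0.64 + 0.64) = 0.5 and the bias is 0.8 × 0.5 × 1 = 0.40. A true worsening of 0.5 then appears as about 0.10, and was detected in about 11% of trials.

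**The case against.** The strongest reply is that hypothesis 3 is defined on the PSS at block start and end, not on pre-session VAS. Shrinkage needs two further conditions: that lower chronic stress lowers the arrival score, and that the session effect depends on that score or meets the floor. This stands. A reader might infer that success on hypothesis 3 necessarily produces a finding of habituation; the documents do not support that, since a parallel fall leaves the difference almost unchanged.

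A reader might also infer that the trial cannot tell boredom from benefit. That is too strong. Section 13.1 collects both VAS readings at every session, the PSS and an interview. If the comparisons in 16.2 were made on pre-session scores, they would show the fall in arrival level directly. The gap is in the stated analysis, not in the data.

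The percentages cannot be read as the plan's error rate. Section 16.2 does not say that change scores are compared, labels those tests carry-over, and does not tie them to hypothesis 4. Section 16.1 does not say that 0.74 is a change-score SD.

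Section 16.2 also defines the relaxing effect as a ratio, 1 minus before over after. Under a strictly proportional effect the ratio stays constant: 1 − 5/3 and 1 − 3/1.8 are both −0.67. This helps in that one case only. It does not hold when the intercept is not zero or the floor binds, and hypothesis 4 specifies the difference.

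Finally, habituation is not an endpoint in section 8. That limits the weight of the point, but section 7.1 still asks the question.

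**Conclusion.** The concern holds in a conditional form. Hypothesis 4 rests on a single measure that can fall through habituation or through cumulative benefit, and nothing in the protocol says how the two will be separated. The conditions under which benefit shrinks the difference may not apply, but the plan has no step to check whether they do.

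The size depends on unknowns. Under the stated assumptions the false-flag rate is about 17% to 71% for slopes 0.8 to 0.4, and about 5% if the scores fall in parallel. The slope, the 1-point fall, independence across sessions and the meaning of 0.74 are assumptions, so these figures show that the problem can matter, not how large it will be. The point concerns the interpretation of the habituation question; the primary endpoint result is unaffected.

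**What to change.** Amend hypothesis 4 and section 16.2 as follows.

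- For each treatment, prespecify a model with session number (1 to 10) as a term and participant random effects. Report the pre-session and post-session VAS trajectories separately, alongside the trend in the difference.
- As a companion analysis, model post-session VAS on session number, adjusted for the same session's pre-session VAS.
- Call a falling difference habituation only when a falling pre-session VAS does not explain it: either pre-session VAS is stable, by a margin fixed in advance, or post-session VAS worsens at a given pre-session VAS. Otherwise report the result as indeterminate.
- Treat the pre-session trend as evidence on cumulative benefit, read with the PSS change and the end-of-block interview.
- State that, when pre-session VAS falls, error in it biases the adjusted trend toward no habituation, so a null adjusted result is not proof that habituation is absent.

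The cost is wording and modest analysis time. No new data, visits or participants are needed. The real downside is that some results will have to be reported as indeterminate.

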### Sub-hypotheses:

1. The difference in effect between standard and VR relaxation will be greater in patients with intellectual disabilities, as they have a less developed capacity for imagination.

2. There are differences in video preferences among patients with different psychiatric disorders. For example, individuals with autism may prefer static videos, while those with borderline personality disorder may prefer interactive videos.
3. The relaxing effect will manifest more quickly when using VR than with standard relaxation.

---

## **7. Objective of the Clinical Investigation**

### **7.1 Primary Objectives**

The main objective is to examine the relaxing effect of VRelax. We aim to measure the magnitude and duration of the effect and assess the difference compared to standard relaxation exercises. What is the immediate effect, and what is the long-term impact? Is there any habituation? Which physiological parameters are most influenced?

### **7.2 Secondary Objectives**

This study also serves to provide a scientifically grounded basis for deciding whether to implement VR in clinical practice. Therefore, we will evaluate applicability, usability, and implementation potential of the technology. Is investment in this relatively expensive technology justified?

Additionally, this study will help identify possible barriers and challenges associated with VR usage. It also serves as a starting point for the implementation of other e-health technologies in the future, with the experience and expertise gained through this study becoming a valuable asset.

---

## **8. Endpoints**

### **8.1 Primary Endpoint**

The primary endpoint is the VAS score for relaxation. We will examine whether there is a change in the relaxation VAS score between the time points before and after a relaxation session, with an average improvement of 0.5 out of 10 considered clinically relevant.

The main goal is to determine whether VR relaxation is an effective method for our population.

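### The documents conflict on whether an uncontrolled pre-to-post VAS change or the VR-versus-standard contrast decides the primary question

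*Combined protocol and SAP*

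**What the plan says.** Five places in the combined protocol and SAP bear on what is primary.

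- **Synopsis.** The primary objective begins "To determine whether VR relaxation has a significant effect on a" and goes on to the person's stress level, assessed among other measures through the VAS relaxation change. No comparator is named. The comparison appears under secondary objectives: "We aim to assess whether VR relaxation has a greater relaxing effect compared to standard relaxation".
- **Section 8.1.** "We will examine whether there is a change in the relaxation VAS score between the time points before and after a relaxation session", with 0.5 out of 10 as the relevant improvement. The section closes with "The main goal is to determine whether VR relaxation is an effective method for our population".
- **Section 7.1.** Under primary objectives, the plan aims to measure the size and duration of the effect and to "assess the difference compared to standard relaxation exercises".
- **Section 16.2.** VAS scores are compared before and after sessions with paired t-tests. A mixed model then estimates VR against standard relaxation, and its Time × Treatment interaction is called the primary parameter. Whether that means primary for the trial or only within that model is not said.
- **Hypotheses.** Hypothesis 1 is pre-post ("VRelax will reduce acute stress: the PRE-VAS score will be higher than the POST-VAS score") and Hypothesis 2 is comparative. Neither is labelled primary.

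Sections 10.1 and 16.1 use an SD for each condition (0.83 standard, 0.74 VRelax), 80% power, alpha 0.05 and 30% dropout to reach 54. Section 10.1 describes the 0.5 as a pre-post improvement.

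**The concern.** This is a randomised crossover, and its strength is that each participant receives both conditions. A pre-post test in the VR block makes no use of that. It asks whether people feel more relaxed after a 20-minute seated VR session than before it, so the non-specific effect of a rest session, or expectation, can be credited to VR.

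The plan itself expects the control to work. Section 6.1 says "While current stress-reducing interventions appear effective", and Hypothesis 4 foresees that "habituation or boredom may occur for both standard and VR relaxation", measured as a shrinking pre-post difference, which presupposes a difference in both conditions. A significant pre-post change under VR is therefore compatible with VR adding nothing to standard relaxation. Section 7.2 asks whether a relatively expensive technology justifies investment, and a pre-post result cannot answer that.

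Two candidate primary tests also leave room to choose between them once results are known. The registration planned before first inclusion (section 18) limits that, but the plan does not name the deciding test.

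**Working it through.** **Inputs.** Difference 0.5, SDs 0.83 and 0.74, alpha 0.05, power 80%, dropout 30% and N = 54 come from sections 10.1 and 16.1. The following are assumptions, because the documents do not state them: two-sided testing, what the SDs are SDs of, all correlations, and one value per person. Power is for a paired t-test, from the noncentral t distribution.

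**1. The plan's figure.** Treat 0.83 and 0.74 as SDs of change, uncorrelated between conditions.
- SD of the VR-minus-standard difference = √(0.83² + 0.74²) = 1.112.
- This needs n = 41 for 80% power; 41 × 1.3 = 53.3, rounded up to 54. The figure is reproduced. (Dividing by 0.7 instead gives 58.6.)

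**2. Does 54 identify the test?** Two other readings give the same SD, and so the same 54.
- Pre-post change of 0.5, pooled single-score SD 0.786, uncorrelated scores: 0.786 × √2 = 1.112.
- Between-condition 0.5, single-score SDs, pre-post r = 0.5, changes uncorrelated between conditions: √(2 × (1 − 0.5) × (0.83² + 0.74²)) = 1.112.

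The pre-post route is fragile. With pre-post r = 0.3 it needs 30 completers (39 enrolled at × 1.3). With 0.74 or 0.83 taken as a change SD, a pre-post test needs only 20 or 24 completers. The number leans towards the between-condition test without proving it.

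**3. What the choice of test does.** Completers: 54 × 0.7 = 37.8, taken as 38. Assume both conditions truly improve by 0.5, so VR adds nothing.

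| Test | SDs are of change | Single-score SDs, pre and post uncorrelated |
|---|---|---|
| VR pre-post | SD 0.74: 98% | SD 0.74√2 = 1.047: 82% |
| Standard pre-post | SD 0.83: 95% | SD 0.83√2 = 1.174: 72% |
| Valid paired between-condition test | 5% | 5% |

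In 40,000 simulated trials, VR passed the pre-post test while the between-condition test was not significant in about 94% (change SDs) or 78% (single-score SDs).

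**4. Power for a between-condition 0.5 with 38 completers, one difference per person.**
- Change SDs: r = 0 (SD 1.112) 77%; r = 0.5 (SD √(0.83² + 0.74² − 0.83 × 0.74) = 0.789) 97%.
- Single-score SDs, changes uncorrelated between conditions: pre-post r = 0 (SD 1.573) 48%; r = 0.3 (SD 1.316) 63%; r = 0.5 (SD 1.112) 77%.
- Averaging ten sessions multiplies the variance by (1 + 9ρ)/10. For an assumed session correlation ρ of 0.8 down to 0.2, power is 85% to over 99% (change SDs, r = 0) and 56% to 95% (single-score SDs, pre-post r = 0).

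**The case against.** The best reply is that section 16.2 already answers the question. The only parameter to which it gives primary status is Time × Treatment, which is the VR-minus-standard difference in pre-to-post change. An endpoint variable defined as a pre-post change is compatible with that contrast, 8.1 speaks of a relaxation session in general and names no test, and the crossover design, section 7.1 and the use of both conditions' SDs point the same way. This stands as a lean, and it rules out saying that the plan has settled on an uncontrolled primary analysis. It does not close the gap. The phrase sits with a model for the comparison that the synopsis calls secondary, no passage links it to the primary endpoint, and 10.1 describes the 0.5 as pre-post.

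Three further limits are fair.

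- A reader might infer that Hypothesis 1 makes the relaxation VAS change primary. It concerns acute stress, carries no primary label, and stands beside the comparative Hypothesis 2.
- A reader might add regression to the mean as a rival explanation. Inclusion has no stress or VAS threshold, so the documents give that little support.
- The pass rates follow from the assumed 0.5 change, and no passage gives the change expected under standard relaxation. If that were 0.25 or 0.1, standard would pass its own pre-post test 44% or 11% of the time (SD 0.83, n = 38).

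It can also be said that naming either test would remove the ambiguity. That is so, but only the between-condition contrast uses the randomised comparison.

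**Conclusion.** The conflict is real and should be resolved before the analysis. The synopsis and 8.1 rest the efficacy question on an uncontrolled change, 7.1 and 16.2 point to the randomised contrast, and nothing says which decides.

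The size is conditional. If both conditions improve by 0.5 with 38 completers and one value per person, the pre-post route declares VR effective 98% or 82% of the time, against 5% for a valid paired between-condition test. The 5% is not claimed for 16.2's model with only a random participant intercept and ten sessions per block, whose error rate depends on variances not given.

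Two stronger readings are not supported. The sample size does not show which test was intended, because 54 fits more than one reading. Nor do the documents show that the trial is underpowered for the contrast: power runs from 48% to over 99% across the assumptions above.

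**What to change.** - **Synopsis, 7.1, 8.1 and 16.2:** name the VR-minus-standard difference in pre-to-post VAS relaxation change (Time × Treatment) as the single primary contrast. Label the within-condition pre-post tests as supportive and not as evidence of VR efficacy. Align the before/after ratio in 16.2 with a contrast stated on the VAS change.
- **10.1 and 16.1:** restate the 0.5 as the between-condition difference, and say what 0.83 and 0.74 are SDs of, which correlation was assumed and how dropout was applied. Restate the power for this contrast at 54 enrolled with 30% dropout.

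**Cost.** Wording in six sections and one recomputed power statement. No new data, change of conduct or added enrolment is proposed. The downsides are that the synopsis ranking is reversed, the efficacy claim becomes harder to meet than with a pre-post test, and the stated power may become less favourable.
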